**Document History – Changes compared to previous final version of SAP**

Date	Time Point	Reasons for update	Outocme for update	Section and title impacted (Current)
31-May-2017	Before DBL	First Version		
01-May-2019	Before DBL	The trial had an early enrollment closure on 12 February 2018; the protocol was amended on April 2018.	The study is now a Phase II trial. All sections related to Efficacy analysis has been removed.  Efficacy data will be summarized by a listing only.	All the sections of the earlier version has been impacted
23-Feb-2020	Before DBL	
 
1. Add one lab param for the shift table.
 
2. Clarify which CRS version will be used.
 
3. For exposure data, GnRH agonist will be combined with ET to report.
 
	
 
1. Blood Creatinine was added to report.
 
2. Added a sentence to use the most up-to-date CRS.
 
3. For exposure data, GnRH was combined with ET to report.
 
	
 
1. Section 4.3
 
2. section 2.7.1.1
 
3. section 2.4.1
 

## List of abbreviations

AE	Adverse event
ATC	Anatomical Therapeutic Classification
CSR	Clinical Study report
CTC	Common Toxicity Criteria
CTCAE	Common Terminology Criteria for Adverse Events
DDFS	Distant disease-free survival
DMC	Data Monitoring Committee
FAS	Full Analysis Set
eCRF	Electronic Case Report Form
iDFS	Invasive disease-free survival
IRT	Interactive Response Technology
LRRFS	Loco-regional recurrence-free survival
MedDRA	Medical Dictionary for Regulatory Activities
NCI	National Cancer Institute
OS	Overall Survival
PPS	Per-Protocol Set
PRO	Patient-reported Outcomes
QoL	Quality of Life
RFS	Recurrence-free survival
SAP	Statistical Analysis Plan
SOC	System Organ Class
TFLs	Tables, Figures, Listings
WHO	World Health Organization

## 1 Introduction

This statistical analysis plan (SAP) describes all planned analysis for the clinical study report(s) (CSR) of study CLEE011G2301, an open label, multicenter, Phase II, U.S based study to evaluate safety of ribociclib with endocrine therapy as an adjuvant treatment in patients with hormone receptor-positive, HER2-negative, high risk early breast cancer.

The content of this SAP is based on protocol CLEE011G2301 version 02. All decisions regarding final analysis, as defined in the SAP document, have been made prior to database lock and unblinding of the study data.

### 1.1 Study design

This was a randomized, phase III, double-blind, placebo-controlled, multi-center, international study to evaluate efficacy and safety of ribociclib with ET as an adjuvant treatment in patients with HR-positive, HER2-negative, high risk early breast cancer.

Following the protocol amendment 02, this study is now an open label, multi-center phase II conducted in the U.S only. The study has been closed to enrollment. All randomized patients were unblinded; patients randomized to placebo permanently discontinued study treatment and patients randomized to ribociclib were offered the option to continue treatment with ribociclib + ET (excluding tamoxifen). Patients randomized to placebo have to complete 30-day safety follow up after the last dose of placebo.

### 1.2 Study objectives and endpoints

Objectives and related endpoints are described in [Table 1-1](#) below.

**Table 1-1 Objectives and related endpoint**

Objective	Endpoint
Primary To evaluate the preliminary safety and tolerability of the ribociclib + ET in patients that were randomized to ribociclib + ET prior to the early closure of enrollment.	Tolerability and Safety of the treatment regimen based on frequency and severity of AEs, laboratory and ECG abnormalities

## 2 Statistical methods

### 2.1 Data analysis general information

The final analysis will be performed by Novartis. SAS version 9.4 or later will be used to perform all data analyses and to generate tables, figures and listings.

#### Data included in the analysis

All data collected up to the last patient last visit will be used in the analysis.

#### General analysis conventions

**Pooling of centers:** Unless specified otherwise, data from all study centers will be pooled for the analysis. Due to expected small number of patients enrolled at centers, no center effect will be assessed. Protocol deviations, number of patients in analysis populations and discontinuations from study treatment will be summarized by center.

**Qualitative data** (e.g., gender, race, etc.) will be summarized by means of contingency tables by treatment group; a missing category will be included as applicable. Percentages will be calculated using the number of patients in the relevant population or subgroup as the denominator.

**Quantitative data** (e.g., age, body weight, etc.) will be summarized by appropriate descriptive statistics (i.e. mean, standard deviation, median, minimum, and maximum) by treatment group.

#### 2.1.1 General definitions

##### Investigational drug and study treatment

*Investigational drug*, will refer to the ribociclib/placebo only. Whereas, *study treatment* will refer to ribociclib + endocrine therapy (ET) and placebo + ET. In this study, ET may include tamoxifen, letrozole, anastrozole or exemestane. For premenopausal women, ET also include GnRH agonist to suppress ovarian function. ET alone after discontinuation of the ribociclib/placebo is not considered a “study treatment”.

The term investigational treatment may also be referred to as *study treatment* which is used throughout this document.

##### Date of first administration of investigational drug

The date of first administration of investigational drug is defined as the first date when a non-zero dose of investigational drug is administered and recorded on the Dosage Administration Record (DAR) (e)CRF. The date of first administration of investigational drug will also be referred as start of investigational drug.

### **Date of last administration of investigational drug**

The date of last administration of investigational drug is defined as the last date when a nonzero dose of investigational drug is administered and recorded on DAR eCRF. The date of last administration of investigational drug will also be referred as end of investigational drug.

### **Date of first administration of study treatment**

The date of first administration of study treatment will be derived as the first date on/after randomization when a nonzero dose of any component of study treatment was administered as per the (e)CRF. (Example: if randomization date is 03-Jan-2015, and 1st dose of ribociclib is administered on 05-Jan-2015, and 1st dose of ET is administered on 03-Jan-2015, then the date of first administration of study treatment is on 03-Jan-2015).

ET prior to and on/after randomization will be entered in the Adjuvant Endocrine Therapy eCRF page. First date on/after randomization of ET will be derived based on the start and end dates in the eCRF. (Example: randomization date is 03-Jan-2015, if ET with non-zero dose has a start date of 15-Dec-2014 and an end date on/after randomization, then first date on/after randomization of ET will be 03-Jan-2015; if ET start date is 15-Dec-2014 and end date is 02-Jan-2015, then restarts non-zero dose on 04-Jan-2015, then first date on/after randomization of ET will be 04-Jan-2015; in special cases in which start date is before randomization and end date is missing, then patient is ongoing and first date on/after randomization of ET will be date of randomization)

### **Date of last administration of study treatment**

The date of last administration of study treatment is defined as the last date when a non-zero dose of study treatment was administered as per (e)CRF. For patients who take at least one dose of ribociclib/placebo, date of last administration of study treatment is the last date when a non-zero dose of ribociclib/placebo was administered. So date of last administration of study treatment is the same as date of the last administration of investigational drug for these patients. For patients who only take ET on/after randomization but no ribociclib/placebo, date of last administration of study treatment is defined as the date of first administration of study treatment.

#### **Study day**

The study day, describes the day of the event or assessment date, relative to the reference start date.

The study day is defined as:

- The date of the event (visit date, onset date of an event, assessment date etc.) – reference start date + 1 if event is on or after the reference start date;
- The date of the event (visit date, onset date of an event, assessment date etc.) – reference start date if event precedes the reference start date.

The reference start date for safety assessments (e.g. adverse event onset, laboratory abnormality occurrence, vital sign measurement, dose interruption etc.) is the start of study treatment.

The reference start date for all other, non-safety assessments (e.g., recurrence assessment,) is the date of randomization.

The study day will be displayed in the data listings. If an event starts before the reference start date, the study day displayed on the listing will be negative.

### **Time unit**

A year length is defined as 365.25 days. A month length is 30.4375 days (365.25/12). If duration is reported in months, duration in days will be divided by 30.4375. If duration is reported in years, duration in days will be divided by 365.25.

### **Baseline**

For efficacy evaluations, the last non-missing assessment, including unscheduled assessments on or before the date of randomization is taken as “baseline” value or “baseline” assessment. In the context of baseline definition, the efficacy evaluations also include PRO and performance status.

For safety evaluations, the last available assessment on or before the date of start of study treatment is taken as “baseline” assessment.

For ECGs, the study requires triplicates per time point. The average of these measurements would be calculated for baseline. In case ribociclib/placebo dosing time is recorded on the date of first dose of study treatment along with the ECG, the last available assessment before the ribociclib/placebo start date/time will be used for baseline.

In rare cases where multiple measurements meet the baseline definition, with no further flag or label that can identify the chronological order, then the following rule should be applied: If values are from central and local laboratories, the value from central assessment should be considered as baseline. If multiple values are from the same laboratory or collected for ECGs or vital signs, then the last value should be considered as baseline. The last value refers to the one with a larger repeated sequence number recorded in the eCRF.

If patients have no value as defined above, the baseline result will be missing.

### **On-treatment assessment/event and observation periods**

For adverse event reporting the overall observation period will be divided into three mutually exclusive segments, based on AE start date:

1. ***pre-treatment period***: from day of patient’s informed consent to the day before first administration of study treatment
2. ***on-treatment period***: from date of first administration of study treatment to 30 days after date of last actual administration of any study treatment (including start and stop date)
3. ***post-treatment period***: starting at day 30+1 after last administration of study treatment.

Safety summaries (tables, figures) include only data from the on-treatment period with the exception of baseline data which will also be summarized where appropriate (e.g. change from baseline summaries). In addition, a separate summary for death including on treatment and post treatment deaths will be provided. In particular, summary tables for adverse events (AEs) will summarize only on-treatment events, with a start date during the on-treatment period (***treatment-emergent*** AEs).

However, all safety data (including those from the post-treatment period) will be listed and those collected during the pre-treatment and post-treatment period will be flagged.

## 2.2 Analysis sets

### Full Analysis Set

The Full Analysis Set (FAS) comprises all patients to whom study treatment has been assigned by randomization. According to the intent to treat principle, patients will be analyzed according to the treatment and strata, they have been assigned to during the randomization procedure.

### Safety

The **Safety set** includes all randomized subjects who received any study treatment (i.e. at least one dose of ribociclib/placebo or ET). Subjects will be analyzed according to the study treatment actually received.

The actual treatment received corresponds to:

- the randomized treatment if patients took at least one dose of that treatment.
- the first treatment received if the randomized treatment was never received

### Patient Classification:

Patients may be excluded from the analysis populations defined above based on the protocol deviations entered in the database and/or on specific subject classification rules defined in [Table 2-2](#).

**Table 2-2 Subject classification based on protocol deviations and non-PD criteria**

Analysis set	Protocol deviations leading to exclusion	Non protocol deviation leading to exclusion
FAS	No written inform consent	Not applicable
Safety set	No written inform consent	No dose of study treatment

### Withdrawal of Informed Consent

Any data collected in the clinical database with a date after a subject withdraws informed consent from all further participation in the trial, will not be included in the analysis. The date on which a patient withdraws full consent is recorded in the eCRF.

Additional data for which there is a separate informed consent, e.g. biomarker etc., collected in the clinical database without having obtained that consent will not be included in the analysis. These data will be excluded by the presence of the appropriate protocol deviation criterion.

## **2.2.1 Subgroup of interest**

### **Efficacy**

Not applicable

### **Safety**

Not applicable

## **2.3 Patient disposition, demographics and other baseline characteristics**

The Full Analysis Set (FAS) will be used for all baseline and demographic summaries and listings unless otherwise specified. Summaries will be reported by treatment arm and for all patients and listings will be reported by treatment arm to assess baseline comparability. No inferential statistics will be provided.

### **Basic demographic and background data**

All demographic and baseline disease characteristics data will be summarized and listed by treatment arm. Categorical data (e.g. gender, age groups, race, ethnicity, region, ECOG Performance Status), will be summarized by frequency counts and percentages; the number and percentage of patients with missing data will be provided. Continuous data (e.g. age, weight, height, body mass index) will be summarized by descriptive statistics (N, mean, median, standard deviation, Q1, Q3, minimum and maximum). BMI (kg/m^2) will be calculated as  $\text{weight}[\text{kg}] / (\text{height}[\text{m}]^2)$  using weight at Baseline.

### **2.3.1 Patient disposition**

Enrollment by country and center will be summarized for all screened patients and also by treatment arm using the FAS. The number (%) of randomized patients included in the FAS will be presented overall and by treatment group.. The number (%) of patients in the FAS who are still on treatment, who discontinued the study phases and the reason for discontinuation will be presented overall and by treatment group.

The following summaries will be provided (with % based on the total number of FAS patients):

- Number (%) of patients who were randomized (based on data from IRT system)
- Number (%) of patients who were randomized but not treated (based on eCRF page not completed for any study treatment component, 'DAR' eCRF page for ribociclib/placebo, 'Adjuvant endocrine therapy' eCRF page for ET and 'GnRH (Gonadotropin-Releasing Hormone) Agonist Therapies' eCRF page for GnRH; for ET and GnRH page, only dose administered on/after randomization will be considered)
- Primary reason for not being treated (based on "End of Treatment Phase Completion" eCRF page)

- Number (%) of patients who were treated (based on eCRF pages of each study treatment component completed with non-zero dose administered)
- Number (%) of patients who are still on-treatment (based on the ‘End of Treatment Phase’ page not completed);
- Number (%) of patients who discontinued the study treatment phase (based on the ‘End of Treatment Phase’ page)
- Primary reason for study treatment phase discontinuation (based on the ‘End of Treatment Phase’ page)

### **Protocol deviations**

The number (%) of patients in the FAS with any protocol deviation will be tabulated by deviation category (as specified in the study Data Handling Plan) overall and by treatment group for the FAS. Major protocol deviations leading to exclusion from analysis sets will be tabulated separately overall and by treatment group. All protocol deviations will be listed.

### **Analysis sets**

The number (%) of patients in each analysis set (defined in [Section 2.2](#)) will be summarized by treatment group.

## **2.4 Treatments (study treatment, rescue medication, concomitant therapies, compliance)**

### **2.4.1 Study treatment adherence/ compliance**

Duration of exposure, will be summarized by treatment arm, for ribociclib/placebo. Exposure summaries for ET and GnRH will also be summarized by treatment arm. Duration of exposure will be categorized into time intervals; frequency counts and percentages will be presented for the number (%) of subjects in each interval.

Subject level listings of all doses administered on treatment (for ET, also after the treatment phase) along with dose change reasons will be produced.

The safety set will be used for all summaries and listings of study treatment.

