### **Duration of exposure to investigational drug, control drug and combination partner**

The study treatment has the following components:

- Investigational drug: ribociclib/placebo
- Combination partner
  - ET: Any of letrozole, anastrozole and exemestane and GnRH agonist

The duration of exposure to ribociclib/placebo, ET will be summarized.

Duration of exposure to ribociclib/placebo and ET (tamoxifen, letrozole, anastrozole, exemestane and GnRH agonist) during the treatment phase will be calculated as:

**Duration of exposure (days) during the treatment phase** = (last date of exposure during the treatment phase) – (first date of exposure on/after randomization) + 1.

The last date of exposure during the treatment phase is defined as follows for ribociclib/placebo and ET:

- For ribociclib/placebo: the last date of exposure is defined as the date of last administration of ribociclib/placebo; the first date of exposure is defined as the date of first administration of ribociclib/placebo
- For ET: the last date of exposure during the treatment phase is defined as the date of last administration of any ET on/before the last date of exposure of ribociclib/placebo; the first date of exposure is defined as the date of first administration of any ET on/after randomization.
- In rare cases in which patient does not have any ribociclib/placebo but have ET on/after randomization, the last date of exposure of ET during the treatment phase is defined as the date of first exposure of ET on/after randomization

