#### **2.4.2 Primary endpoint**

The primary endpoints of this study are the tolerability and safety of the treatment regimen based on frequency and severity of AEs, laboratory and ECG abnormalities. Descriptive summaries of key safety and baseline characteristics will be provided. These include summaries of treatment duration exposure, adverse events, labs, and ECG findings. The details can be found in [section 2.7](#).

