##### **2.7.1 Adverse events (AEs)**

AE summaries will include all AEs occurring during on treatment period. All AEs collected in the AE (e)CRF page will be listed along with the information collected on those AEs e.g. AE

relationship to study drug, AE outcome etc. AEs with start date outside of on-treatment period will be flagged in the listings.

AEs will be summarized by number and percentage of subjects having at least one AE, having at least one AE in each primary system organ class (SOC) and for each preferred term (PT) using MedDRA coding. A subject with multiple occurrences of an AE will be counted only once in the respective AE category. A subject with multiple CTCAE grades for the same preferred term will be summarized under the maximum CTCAE grade recorded for the event. AE with missing CTCAE grade will be included in the 'All grades' column of the summary tables.

In AE summaries, the primary system organ class will be presented alphabetically and the preferred terms will be sorted within primary SOC in descending frequency. The sort order for the preferred term will be based on their frequency in the ribociclib + ET arm.

The following adverse event summaries will be produced by treatment arm; overview of adverse events and deaths (number and % of subjects who died, with any AE, any SAE), AEs by SOC and PT, summarized by relationship (all AEs and AEs related to study treatment), seriousness (SAEs and non-SAEs), leading to treatment discontinuation, and leading to fatal outcome. In addition, a summary of serious adverse events with number of occurrences will also be produced (an occurrence is defined as >1 day between start and prior end date of record of same preferred term).

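### Tolerability is a primary endpoint, but dose reductions and interruptions are only listed, and no table of AEs leading to dose adjustment or interruption is planned

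*SAP*

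**What the plan says.** Table 1-1 gives the primary endpoint as "Tolerability and Safety of the treatment regimen based on frequency and severity of AEs, laboratory and ECG abnormalities", and section 2.4.2 repeats it. Section 2.4.2 then names the descriptive summaries that serve it: treatment exposure, adverse events, laboratory results and ECG findings.

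On dosing, section 2.4.1 plans one kind of summary table: "Duration of exposure will be categorized into time intervals; frequency counts and percentages will be presented". Duration is the difference "last date of exposure during the treatment phase) – (first date of exposure on/after randomization) + 1" (the opening bracket is omitted here). Individual doses go elsewhere: "Subject level listings of all doses administered on treatment (for ET, also after the treatment phase) along with dose change reasons will be produced". The section heading refers to adherence and compliance, but the section defines no measure of either. Dose intensity is not mentioned anywhere in the SAP.

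On adverse events, section 2.7.1 plans tables by SOC and PT for all and related events, and by "seriousness (SAEs and non-SAEs), leading to treatment discontinuation, and leading to fatal outcome". On severity it says: "A subject with multiple CTCAE grades for the same preferred term will be summarized under the maximum CTCAE grade recorded for the event".

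**The concern.** Under a drug given over a long period, patients can show poor tolerance in two ways that fall short of stopping: their dose is lowered, or it is held for a time. Section 2.1.1 recognises this to a degree, since its study-day rule gives dose interruption as an example of a safety assessment. No analysis is attached to that example.

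Safety and tolerability are what this report can deliver, because the document history says that efficacy data will be summarised by a listing only. If the report is to say how many patients needed a reduction or interruption, and for which events, the SAP provides no table to support it. Any such figure would be counted from the listing after the fact, with no prior rule for what counts as a reduction or an interruption.

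**Working it through.** The SAP states no sample size, power or other figure on this point, so there is nothing to reproduce. The check is to go through the planned outputs and ask which of them change when a dose is reduced or interrupted.

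**1. Exposure duration (section 2.4.1).** Let F be the date of first dose, L the date of last dose, z the number of zero-dose days between them, and d the dose level.

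- Planned measure: D = L − F + 1.
- Days on which drug was taken: D − z.

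Neither z nor d enters D. Two patients with the same F and L have the same D whatever their z and d. Section 2.1.1 defines the last administration by a non-zero dose, so days off drug after the final dose are not counted. Gaps before it are. The measure is a correctly labelled duration, but it cannot show dose modification.

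**2. Dose changes and their reasons (section 2.4.1).** These go to a subject-level listing. No count, percentage or breakdown by reason is defined.

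**3. AE tables by consequence (section 2.7.1).** Two are planned: "leading to treatment discontinuation, and leading to fatal outcome". None covers dose reduction or interruption. Take two patients with the same event at the same maximum grade, one managed without a dose change and one with repeated interruptions. They contribute the same row to the SOC and PT tables and, with the same F and L, the same duration.

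**4. Disposition (section 2.3.1).** Number (%) who discontinued the treatment phase, with primary reason. This captures permanent discontinuation only.

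**5. Tables for the endpoint's named components.** AEs with maximum CTCAE grade (section 2.7.1), AESI groupings (2.7.1.1), laboratory shift tables and liver thresholds (2.7.3), and notable ECG values (2.7.4.1). These do quantify toxicity that does not end in discontinuation. They do not record whether the dose was changed because of it.

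**Result.** Items 1, 3, 4 and 5 contain no summary of dose modification. Item 2 contains the information, but only patient by patient.

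**The case against.** The strongest reply is that the SAP defines its own endpoint and analyses it in full. Tolerability and safety are to be judged on "tolerability and safety of the treatment regimen based on frequency and severity of AEs, laboratory and ECG abnormalities", dose modification is not among these, and every named component has a table. The dose data are not lost either, because each dose and change reason is listed. After early closure of enrolment, and with only a preliminary safety aim left, a listing can be defended. The protocol is not at hand, so whether it calls for dose-modification summaries cannot be checked. Section 3 of the SAP says only that nothing changed from the protocol-specified analysis.

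Much of this stands. It rules out two stronger readings that a reader might infer:

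- *The plan cannot quantify tolerability short of permanent discontinuation.* The graded AE, laboratory and ECG tables do so, as the endpoint definition requires.
- *The tables err in the drug's favour.* Duration of exposure is labelled as duration and does not claim to measure drug taken. AE percentages are percentages of patients and do not use duration as a denominator, so no bias in AE rates follows. Nor can a size be put on the days off drug: the SAP gives no dosing schedule, so planned off-drug days cannot be separated from those due to intolerance.

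The reply does not remove the narrower point. Section 2.4.2 itself brings exposure in to support the primary endpoint, and the only exposure table chosen cannot show dose modification. Choosing tables and derivations is the work of a SAP. Section 2.4.1 does choose here: it assigns dose changes and their reasons to a listing.

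**Conclusion.** The point holds as a limited gap in the choice of outputs. It is not a contradiction of the endpoint definition and not an error in any planned rate. Tolerability shown through dose reduction or interruption is recorded but not summarised: of the planned summary tables, none counts patients with a reduction or an interruption, and none counts AEs that led to one.

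Its size in patients or days cannot be stated, because the documents give no dose-modification data and no planned schedule.

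The conclusion rests on the SAP text alone. It would weaken if the protocol, or an output specification outside the SAP, already required these tables. This is a cheap improvement worth making before database lock.

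**What to change.** In section 2.4.1, on the safety set, by arm and for ribociclib/placebo, add:

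- number (%) of patients with at least one dose reduction, overall and by recorded reason;
- number (%) of patients with at least one dose interruption, overall and by recorded reason;
- a rule for identifying each from the dosing records, under which planned off-drug days are not counted as interruptions;
- relative dose intensity (dose taken divided by dose planned), if the planned dose is taken from the protocol, since the SAP does not state it.

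In section 2.7.1, add a table by SOC and PT of AEs leading to dose adjustment or interruption. This assumes that the AE page records the action taken for dose changes. The planned table of AEs leading to discontinuation suggests that such a field exists, but the SAP does not say so, and it should be confirmed first.

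The cost is two extra tables, or three with relative dose intensity, plus the short derivation rule. Doses and dose-change reasons are already collected for the listing, so no new data are expected. The existing duration table and listing can stay as they are.
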